	Catheter breakage	Breakage of the catheter used to deliver Lava, resulting in a luminal catheter defect at the portion of the catheter that resided within the subject's vasculature. Kinks are not considered breakage. Breaks of other catheters, sheaths, and guides do not trigger this component of the composite MAE endpoint.
	Catheter entrapment	Inability to extract the catheter used for Lava delivery, due to adherence to the Lava material, requiring endovascular or open surgical intervention to remove the catheter or retained pieces of the catheter. The endpoint is triggered if pieces of the catheter are retained in the subject's vasculature at the conclusion of the index procedure.
Non-Target Territory		A vascular territory outside of the planned Target Territory specified by the Investigator prior to embolization at that site. Inadvertent embolization of Lava to a Non-Target Territory is an element of the composite MAE endpoint.
Procedure-Related		A procedure-related event is an event that occurs during the index procedure or within 30 days of the index procedure-irrespective of causation but not otherwise classified as a device-related event (i.e. an event that is device-related need not also be reported as procedure-related). As well, procedure-related adverse events include any events related to a remedial procedure necessary to treat the target territory (e.g. a rebleeding episode). An event related to a prior procedure-related event is also considered to be procedure-related.
Reintervention		Defined as those secondary procedures, endovascular or open surgical, that occur after the subject has left the angiography suite after the index procedure and are performed as a result of residual bleeding, recurrent bleeding, or a device- or procedure-related events.
Serious Adverse Event		An adverse event where the outcome is one of the following: 1. Death; 2. Life-threatening, where the patient was at substantial

Category	Term	Definition
		
risk of dying or continued use of the product might have resulted in death;
 
 
3. Hospitalization or prolongation of an existing hospitalization;
 
4. Disability or permanent damage, interfering with the patient's ability to conduct normal life functions;
 
5. Congenital anomaly or birth defect;
 
6. Required intervention to prevent permanent impairment.
 

Target Lesion		A hemorrhage site planned for embolization with the Lava LES, as specified by the Investigator at the index procedure after diagnostic angiography but prior to embolization of that area. Up to 4 Target Lesions may be treated in a subject.
Target Territory		The vascular territory supplied by a Target Vessel, within a single organ, extremity, or tissue bed
Target Vessel		A vessel in which the tip of the delivery catheter is located at the time Lava administration is begun. More than one Target Vessel may supply a Target Lesion.
Technical Success		Absence of angiographic evidence of bleeding in the Target Lesion at the conclusion of the index procedure.
Unanticipated Adverse Device Effect		Any serious adverse effect on health or safety or any life-threatening problem or death caused by, or associated with, a device, if that effect, problem, or death was not previously identified in nature, severity, or degree of incidence in the investigational plan.
Unscheduled Visits		Unplanned visits prompted by recurrent bleeding or a site-reported device- or procedure-related complication.

[REDACTED]

---

## 1 PROTOCOL SUMMARY

### 1.1 SYNOPSIS

Title:	Liquid Embolization of Arterial Hemorrhages in the Peripheral Vasculature The LAVA Study
Study Description:	This statistical analysis plan (SAP) is for a prospective, multicenter, single-arm study of the Lava™ Liquid Embolic System (LES) for the embolic treatment of arterial hemorrhage in the peripheral vasculature compared to performance goals.
Objectives:	To evaluate the safety and effectiveness of the Lava LES for the embolic treatment of arterial hemorrhage in the peripheral vasculature. The study will test the proportion of Target Lesions with 30-day Clinical Success against a 72% performance goal and test the proportion of subjects experiencing freedom from 30-day major adverse events against a 82% performance goal both tests using a one-sided exact confidence interval and one-sided alpha level of 0.025.
Endpoints:	
Primary Safety Endpoint:
 
The primary safety endpoint is a composite of freedom from 30-day Major Adverse Events (MAEs). MAEs include the following events as adjudicated by an independent Clinical Events Committee (CEC):
 

1. Ischemia or infarction of the target territory;

2. Non-target embolization;

3. Allergic reactions to Lava;

4. Catheter breakage;

5. Catheter entrapment defined as the inability to withdraw a catheter from adherence to Lava.

 
Primary Effectiveness Endpoint:
 
The primary effectiveness endpoint is Clinical Success, defined as absence of bleeding from the target lesion after embolization with the Lava LES, without the need for emergency surgery, re-embolization, or other target lesion reinterventions within 30 days of the index procedure. Absence of bleeding is defined as no BARC Type 3 or greater bleeding occurring after the index procedure, either persistent or recurrent.

Study Population:	The study will enroll 113 male and female US subjects at least 18 years of age with active arterial bleeding from the peripheral vasculature, excluding those with bleeding from the vessels of the heart, intracranial vasculature, intra-dural bleeding in the spinal canal, and post-partum hemorrhage.
Phase:	This is a pivotal Investigational Device Exemption (IDE) study.
Description of Study	Lava is an injectable, non-adhesive liquid embolic agent comprised of ethylene vinyl alcohol (EVOH) copolymer dissolved in dimethyl sulfoxide
Treatment:	

(DMSO) and suspended micronized tantalum powder to provide contrast for visualization under fluoroscopy. Lava is first prepared with the Lava Mixing Kit and then delivered to the target anatomy via a DMSO compatible microcatheter. The Lava precipitates into a spongy, coherent mass or cast upon exposure to blood at the targeted location. Lava LES is manufactured by BlackSwan Vascular, Inc. The adjunctive devices, including guidewires, sheaths, guides, and catheters are not supplied by BlackSwan Vascular, Inc.; these will be chosen at the Investigator's discretion from currently marketed devices.

**Study Duration:** It is estimated that enrollment will take 12 months, subjects will be followed for 30 days and data analysis will take 3 months for a total of 16 months study duration.

**Participant Duration:** The institutional Principal Investigator (PI), treating physician or experienced personnel should conduct a close follow-up with scheduled patient visits and examinations as needed.

## 2 ENDPOINT DEFINITIONS

The primary safety endpoint is a composite of freedom from 30-day MAEs. MAEs include the following events as adjudicated by an independent Clinical Events Committee (CEC);

1. Ischemia or infarction of the target territory;
2. Non-target embolization;
3. Allergic reactions to Lava;
4. Catheter breakage;
5. Catheter entrapment.

Each MAE element is determined after enrollment; any events that occur prior to the point of enrollment are not included in the primary safety endpoint. The target territory or territories are specified by the Investigator at the time of enrollment; embolization to a non-target territory is defined as unintentional administration of Lava to a vascular bed outside of a target territory. Catheter breakage refers to defects in the luminal continuity of the microcatheter used to deliver Lava, but not to other catheters that may be used in other aspects of the procedure separate from the administration of Lava. Catheter kinks without defects in luminal continuity will not trigger the endpoint. Catheter entrapment, defined as the inability to withdraw the catheter refers to the catheter with which Lava is administered and is defined by the need for endovascular or open surgical procedures to remove the catheter or portions thereof. Retained portions of the catheter trigger the endpoint, irrespective whether additional endovascular or open surgical procedures were performed.

The primary effectiveness endpoint is Clinical Success, defined as absence of bleeding from the target lesion after embolization with the Lava LES, without the need for emergency surgery, re-embolization, or other target lesion reinterventions within 30 days of the index procedure. Absence of bleeding is defined as no BARC Type 3 or greater bleeding occurring after the index procedure, either persistent or recurrent. The ascertainment of persistent or recurrent BARC Type 3 or greater bleeding does not include bleeding that occurred prior to the conclusion of the index procedure.

The primary effectiveness endpoint will be adjudicated by the CEC, relying on information from the source documents and/or the core laboratory findings of absence of bleeding. Effectiveness relates to the target lesion(s) as defined by the Investigator at the index procedure.

The following measures will be assessed as secondary endpoints of the study:

1. Technical Success, defined as absence of angiographic evidence of bleeding from the target lesion at the conclusion of the index procedure;
2. Successful delivery of Lava and intact retrieval of the microcatheter;
3. Assessment of each element of the primary safety endpoint (MAE) as an individual component within 30 days of the index procedure;
4. Symptomatic ischemia in the target territory that does not require intervention within 30 days of the index procedure;
5. All-cause mortality within 30 days of the index procedure;
6. Bleeding-related mortality (attributable to bleeding in a target territory) within 30 days of the index procedure;
7. Open surgical conversion for persistent or recurrent bleeding within 30 days of the index procedure;
8. Device-related serious adverse events within 30 days of the index procedure;
9. Procedure-related serious adverse events within 30 days of the index procedure;

 The effectiveness endpoint is lesion-based and not subject-based. Failure of the effectiveness endpoint is triggered by events that are referable to the specific lesion and not to other events referable to another lesion in the same subject. For example, if a subject has two lesions where the first is treated successfully but the other rebleeds and requires emergency surgery, effectiveness would have been achieved in the first lesion but not in the second.

 Core laboratory-determined assessment of bleeding is used for the primary and secondary endpoints. If core laboratory images are unavailable or uninterpretable, the site-reported determinations will be used.

10. Access site hematoma (>5cm in longest axis) within 30 days of the index procedure;
11. Access site false aneurysm within 30 days of the index procedure;
12. Units of red blood cells transfused after administration of Lava;
13. Duration of the index procedure, total and after administration of Lava;
14. Contrast administered the during index procedure;
15. Fluoroscopy time during the index procedure;
16. Length of stay in the intensive care unit after the index procedure;
17. Length of hospitalization, total and after the index procedure.

### 3 STATISTICAL CONSIDERATIONS

#### 3.1 STATISTICAL HYPOTHESES

Success or failure of the study will be based on the primary effectiveness and safety endpoints, with descriptive assessment of the secondary safety endpoints.

The primary effectiveness endpoint of Clinical Success will be assessed for all Target Lesions in the Completed Cases dataset and will be calculated on a per lesion basis.

$H_0: P_E \leq PG_E$ , versus

$H_A: P_E > PG_E$ ,

where  $P_E$  is the proportion of Target Lesions with Clinical Success and  $PG_E$  is the effectiveness performance goal of 72%.

The primary safety endpoint of freedom from major adverse events will be assessed for all subjects in the ITT population. The null and alternative statistical hypotheses for the primary safety endpoint will be defined as follows:

$H_0: Ps \leq PG_S$  versus

$H_A: Ps > PG_S$ ,

 As measured on a duplex ultrasound study, assessed by the Core Laboratory.

where  $P_s$  is the population primary safety success rate in the Test group and  $PG_s$  is the safety performance goal of 82%.

The study will be deemed successful if both the primary effectiveness and primary safety hypotheses are met. For the primary effectiveness endpoint, the lower limit of the one-sided 97.5% confidence interval must be greater than 72%. For the primary safety endpoint, the lower limit of one-sided 97.5% confidence interval must be greater than 82%.

### 3.2 SAMPLE SIZE DETERMINATION

A literature search identified 67 publications reporting outcome for 2102 patients treated with embolotherapy for peripheral arterial hemorrhage. A variety of embolic agents were used in the publications. Results were tabulated for technical success, clinical success, 30-day mortality, rebleeding, and non-target territory ischemia. Weighted averages were calculated as the number of patients with a specific type of event, divided by the number of patients with evaluable observations for that event type.

The safety performance goal is based on the available data from the literature review, as well as the Society of Interventional Radiology (SIR) Quality Improvement Guidelines for Percutaneous Embolization document. The SIR document estimated a 2.5% to 8.0% (average 4.0%) rate of symptomatic ischemia after embolotherapy, and a non-target territory embolization rate of approximately 2.5%. Assuming a 1% rate for each of the three other MAE elements (allergic reaction to embolic agent, catheter breakage, inability to withdraw the catheter), a composite rate of 10% was estimated for the 30-day MAE primary safety endpoint. Based on this, a safety success rate analysis was estimated in the range of 88%-92%. Using the sample size of 101 subjects derived for the study hypothesis for primary effectiveness, one-sided 97.5% lower Wilson-score confidence limits were calculated based on safety success rates in the clinical study varying in the range of 88.1%-92.1% and shown in **Table 1** below. Assuming that the safety success rate is 90.1% and the sample size is 101, the lower 97.5% confidence limit is 82.7%. Based on this analysis, a prespecified performance goal for the above-mentioned safety endpoint was chosen to be 82%.

The literature review was performed by BlackSwan Vascular and was included in the preparatory materials for the Q-submission meeting on June 7, 2019 (Q181438/S002).

Table 1. Lower Confidence Limit for Varying Safety Success Rates

Sample Size	# of Successes	Safety Success Rate	Lower 97.5% Wilson Score Confidence Limit
101	93	92.1%	85.1%
101	92	91.1%	83.9%
101	91	90.1%	82.7%
101	90	89.1%	81.5%
101	89	88.1%	80.4%

The objective of Lava LES embolotherapy is to occlude feeding vessels to bleeding target lesions. Clinical Success, the primary effectiveness endpoint, averaged approximated 80% in the 51 publications that reported the endpoint. This rate was consistent with the expected outcomes reported in the Society of Interventional Radiology document. An 8% margin was used to assign the effectiveness performance goal of 72%.

The study is powered for the primary effectiveness endpoint of Clinical Success. Based upon a one-sided exact binomial test using a significance level of 0.025, the literature-derived performance goal of 72%, and an anticipated observed success rate of 84%, the required sample size to achieve a level of 80% power is 101 Target Lesions. Assuming a 10% attrition rate through 30 days, a total of 113 subjects will need to be enrolled.

 The anticipated Clinical Success rate of 84% was estimated after discussions with the Sponsor's scientific advisors.

**Table 2. Sample Size – Primary Effectiveness Endpoint**

Clinical Success	
Performance Goal	72%
Anticipated Clinical Success rate	84%
Significance level	.025
Statistical test	One-sided exact binomial test
Desired power level	80%
Required sample size (Target Lesions)	101
Target Lesions required, assuming 10% attrition through 30 days	113

Calculations for the required sample size for the anticipated success rate for Clinical Success, ranging from 80% to 85% appear in **Table 3**, below.

**Table 3. Sample Size Estimates for Varying Rates of Anticipated Success with the Lava LES**

One-sided Alpha	Power	Clinical Success ( $H_0$ )	Anticipated Success ( $H_A$ )	Sample Size Estimate	Sample Size with 10% Attrition
0.025	80%	72%	80%	227	253
0.025	80%	72%	81%	179	199
0.025	80%	72%	82%	142	158
0.025	80%	72%	83%	118	132
0.025	80%	72%	84%	101	113
0.025	80%	72%	85%	79	88

### 3.3 POPULATIONS FOR ANALYSES

The intention to treat (ITT) dataset, defined as all consented subjects in whom the Lava LES study device entered the vasculature irrespective of adherence with the entry criteria, treatment received, subsequent withdrawal, or deviation from the protocol, will be used for all safety endpoints. Each safety-related endpoint will be assessed on a subject-level basis; expressed as the number of subjects

experiencing at least one event divided by the number of subjects with evaluable observations (see 3.4.1 handling of missing data).

The complete cases (CC) dataset, defined as all ITT subjects who complete 30-day follow-up, will be used for all effectiveness endpoints. Categorical effectiveness endpoints will be expressed as the number of Target Lesions meeting the effectiveness criteria divided by the number Target Lesions with evaluable observations (completed 30-day follow-up). Certain effectiveness endpoints will be assessed on a lesion-level basis; for example, the primary effectiveness endpoint of Clinical Success. Other effectiveness endpoints will be assessed at the subject level; for example, measures related to resource utilization including procedure duration, contrast volume administered, and fluoroscopy time.

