### 6.6.3 Completed Cases Population

The Completed Cases (CC) population will include all ITT subjects who complete 30-day follow-up. The CC population will also include ITT subjects who experience failure of the primary effectiveness endpoint prior to the beginning of the 30-day follow-up timepoint, irrespective of their length of follow-up.

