### **Handling of Missing Data**

All attempts will be made to limit the amount of missing data. For all analyses of the primary endpoints, the number of observations available will be reported so the reader can assess the impact of missing data. In general, and for the primary endpoint analyses, missing data will not be imputed and analyses will be based on available data. For missing values on the primary safety endpoint, an adjustment to the denominator will be made based on the amount of evaluable data. For each visit (or reporting time point), the occurrence rate will be calculated as the number of subjects with certain endpoint occurrence term over the number of evaluable subjects. The evaluable subjects at each reporting time point include all subjects who are enrolled by the snapshot date and

- 1) had an endpoint occurrence within (on or before) the reporting cutoff days (30 days), or
- 2) had a follow-up at or after the lower limit of the reporting window (23 days), or
- 3) the withdrawal consent date/recorded lost-to-follow-up date at or after the lower limit of the reporting window.

Sensitivity analyses will be performed to assess the impact of missing data and potential correlation in the data for the primary endpoints. Three different sensitivity analysis are planned: (1) As described in the protocol, Target Lesions with unavailable effectiveness data will be assumed to have missing data at random and will be imputed by random selection with replacement of data from Target Lesions with complete data. (2) A tipping point analysis will be conducted in which lesions or subjects censored without an event prior to 30 days follow-up are sequentially imputed as failures at the time of censoring. (3) A generalized estimating equation (GEE) logistic regression model will be used to estimate clinical success taking into account potential correlation of multiple Target Lesions within a subject using an exchangeable working correlation structure. The analyses for all the secondary endpoints will not include imputation for missing data, and no formal statistical hypotheses will be tested.

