#### 3.4.2 ANALYSIS OF THE PRIMARY ENDPOINT

Success or failure of the study will be based on the primary effectiveness and safety endpoints, with descriptive assessment of the secondary safety endpoints. The primary effectiveness endpoint of Clinical Success will be assessed for all Target Lesions in the Completed Cases dataset and will be calculated on a per lesion basis.

$H_0: P_E \leq PG_E$ , versus

$H_A: P_E > PG_E$

Where  $P_E$  is the proportion of Target Lesions with Clinical Success and  $PG_E$  is the effectiveness performance goal of 72%.

The primary safety endpoint of freedom from major adverse events will be assessed for all subjects in the ITT population. The null and alternative statistical hypotheses for the primary safety endpoint will be defined as follows:

$H_0: Ps \leq PG_s$  versus

$H_A: Ps > PG_s$ ,

where  $Ps$  is the population primary safety success rate in the Test group and  $PG_s$  is the safety performance goal.

The study will be deemed successful if both the primary effectiveness and primary safety hypotheses are met. For the primary effectiveness endpoint, the lower limit of the one-sided 97.5% confidence interval must be greater than 72%. For the primary safety endpoint, the lower limit of one-sided 97.5% confidence interval must be great than 82%. Handling of missing data is described in section 3.4.1.

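### SAP 3.3 omits the Protocol rule that keeps early effectiveness failures in Completed Cases, so a known failure without a 30-day visit can leave the co-primary denominator

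*SAP*

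**What the plan says.** Protocol 6.6.3 builds the Completed Cases population from two groups. The first is ITT subjects who complete 30-day follow-up. The second is ITT subjects who "experience failure of the primary effectiveness endpoint prior to the beginning of the 30-day follow-up timepoint, irrespective of their length of follow-up".

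SAP 3.3 has only the first group: "The complete cases (CC) dataset, defined as all ITT subjects who complete 30-day follow-up, will be used for all effectiveness endpoints". It then restates the restriction for lesions. A categorical effectiveness endpoint is the number of successful Target Lesions "divided by the number Target Lesions with evaluable observations (completed 30-day follow-up", the closing words being a parenthesis that explains what evaluable means.

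SAP 3.4.2 runs the co-primary test in this set: "The primary effectiveness endpoint of Clinical Success will be assessed for all Target Lesions in the Completed Cases dataset". It adds: "Handling of missing data is described in section 3.4.1".

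In SAP 3.4.1, the general statement for primary endpoints is that "missing data will not be imputed and analyses will be based on available data". A denominator rule follows, introduced by: "For missing values on the primary safety endpoint, an adjustment to the denominator will be made based on the amount of evaluable data". That rule counts as evaluable any subject with an endpoint event by day 30, with follow-up from day 23 on, or with a recorded exit from day 23 on. The tipping-point analysis is for cases in which "lesions or subjects censored without an event prior to 30 days follow-up are sequentially imputed as failures".

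**The concern.** The two documents give different denominators for a co-primary endpoint. Under the Protocol, a lesion known to have failed stays in. Under SAP 3.3, it stays in only if the subject goes on to complete the 30-day visit.

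The clear case is fatal bleeding from a target lesion. The Protocol's definitions make BARC Types 3 to 5 an endpoint trigger, and Type 5 is fatal bleeding. A subject who dies this way before the visit window opens on day 23 is a certain failure with no 30-day visit. A rebleed or reintervention followed by withdrawal is a second case.

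These lesions are failures by definition. With one lesion per subject, removing them raises observed Clinical Success, and the study could meet the 72% goal in the SAP set while missing it in the Protocol set.

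The planned sensitivity analyses do not clearly put them back. The random-draw imputation is for lesions whose outcome is unavailable, the tipping point is for those without an event, and the GEE model addresses correlation between lesions.

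**Working it through.** **Inputs.** One-sided alpha 0.025 with an exact confidence interval, and success if the lower limit exceeds 72% (SAP 1.1, 3.1). Anticipated success 84%, 80% power, 101 Target Lesions, 113 after 10% attrition (SAP 3.2). The share of failures that are known but do not complete is not in the documents, so it is varied.

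**The plan's own figure.** For each n, take the smallest r with P(X ≥ r | n, 0.72) ≤ 0.025, then power = P(X ≥ r | n, 0.84). The smallest n with power of at least 80% is 101, with r = 82, actual alpha 0.0227 and power 81.9%. Then 101/0.90 = 112.2, rounded up to 113. Both figures reproduce.

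**Step 1: how many omitted failures change the result.** The exact (Clopper-Pearson) lower limit for x successes in n is the 0.025 quantile of Beta(x, n − x + 1). Take 101 completers with one lesion each, and add back the known failures that SAP 3.3 leaves out:

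| SAP set | Lower limit | Known failures restored | Protocol set | Lower limit |
|---|---|---|---|---|
| 82/101 | 72.19% (pass) | 1 | 82/102 | 71.35% (fail) |
| 83/101 | 73.30% (pass) | 2 | 83/103 | 71.62% (fail) |
| 84/101 | 74.42% (pass) | 3 | 84/104 | 71.87% (fail) |
| 85/101 | 75.55% (pass) | 5 | 85/106 | 71.32% (fail) |

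**Step 2: effect on the false-pass rate.** Take 113 independent lesions, true success exactly 72%, and total attrition held at 10%. Let q be the share of failures that are known but do not complete. Let b be the remaining loss, unrelated to outcome and missing under both documents, with b + (1 − b)(0.28)q = 0.10.

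- SAP text: a lesion is retained with probability 0.90, and success among retained lesions is 0.72/(1 − 0.28q).
- Protocol rule: a lesion is retained with probability 1 − b, and success among retained lesions is 0.72.
- Pass probability = sum over n of P(n of 113 retained) × P(lower limit > 72% given n).
- Mean known failures dropped = 113 × 0.28 × (1 − b) × q.

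| q | b | Mean dropped | Success rate in SAP set | False pass, SAP text | False pass, Protocol rule |
|---|---|---|---|---|---|
| 0 | 0.1000 | 0 | 72.0% | 1.9% | 1.9% |
| 5% | 0.0872 | 1.4 | 73.0% | 3.1% | 1.9% |
| 10% | 0.0741 | 2.9 | 74.1% | 5.2% | 1.9% |
| 20% | 0.0466 | 6.0 | 76.3% | 12.9% | 2.0% |

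The SAP rate passes 2.5% at q of about 2.8%, or 0.8 lesion on average.

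**The case against.** **The SAP can be read as keeping these failures.** An adjudicated failure is available data. After its opening sentence on safety, the evaluability rule in SAP 3.4.1 uses general terms and keeps anyone with an event by day 30. SAP 3.4.2 covers both co-primaries and sends missing data to 3.4.1. The tipping point treats only event-free exits as missing. The SAP keeps the name Completed Cases and announces no change, although Protocol 7.12 requires changes to be documented.

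This stands as evidence of intent: the Protocol rule was probably meant. It does not settle the text. The rule in 3.4.1 is introduced for safety and counts subjects, and Protocol 7.7 gives the matching rule for safety analyses only. SAP 3.3 refers to 3.4.1 only for safety and gives effectiveness its own parenthesis, which is the more specific wording. Basing an analysis on available data cannot readmit a subject whom the population definition excludes.

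**The number may be small.** The visit can be by telephone between days 23 and 37, and life expectancy over 30 days is required. At q = 2% (0.6 lesion on average) the false-pass rate is 2.3%, still under 2.5%. The 12.9% needs 6.0 known failures among about 11.3 lost lesions (113 × 0.10), over half of all attrition. This also stands.

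**Stronger readings that the documents do not support.**
- A reader might infer that the exclusion can never lower the success rate. SAP 3.3 removes whole subjects, so successful lesions in the same subject leave too. Removing a subject with 3 successes in 4 lowers the rate when the overall rate is below 75%. Near the pass boundary, about 81%, the effect is upward.
- A reader might count aborted procedures and investigator withdrawals (Protocol 8.8) as dropped failures. Neither is an endpoint failure in itself, and subjects converted to surgery must still be followed.
- A reader might charge all failures among the lost to this defect. Those never ascertained are missing under both documents and are a separate question of informative loss.

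**Conclusion.** The point holds. As written, SAP 3.3 contradicts Protocol 6.6.3 on the denominator of a co-primary endpoint and, near the decision boundary, errs in the favourable direction. It should be corrected before analysis.

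The textual discrepancy needs no assumption. The size does: one lesion per subject in Step 1, and independent lesions, a fixed 10% total attrition and an assumed q in Step 2. The documents give no rate for q, so the false-pass figures show sensitivity and do not predict what will happen. What can be said without q is that a single omitted failure is enough to turn 82/101 from a fail into a pass.

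A reader might infer that the sponsor chose to drop failures. The documents do not show that; they show an omission and an internal ambiguity that two programmers could resolve differently.

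**What to change.** In SAP 3.3, restore the second sentence of Protocol 6.6.3. Change the parenthesis so that a Target Lesion is evaluable if 30-day follow-up was completed or if an earlier primary effectiveness failure was adjudicated. In SAP 3.4.1, state that a Target Lesion with an adjudicated effectiveness failure is evaluable.

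The cost is wording; 101 and 113 do not change. The downside is some conservatism, because known failures are kept while some successes are lost. At true success 84% with 113 lesions, power is about 80% if 10% of both successes and failures are lost. With 10% of successes lost, it is about 74% if half of the lost failures are known (expected rate 0.756/0.908 = 83.3%) and about 67% if all are known (0.756/0.916 = 82.5%). The Protocol rule already carries this cost.

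Two further points are optional and separate, because they go beyond restoring the Protocol:
- Protocol 6.6.3 stops at the start of the 30-day timepoint (the window opens on day 23). Extending the cut-off to day 30 would match the endpoint, and should be declared as a change.
- Neither document says how the other lesions of an early-failing subject are counted. This can matter. Starting from 82/101 and adding one early-failing subject, excluding that subject's other lesions gives 82/102 (fail). Counting one, two or three of them as successes gives 83/103 (71.62%, fail), 84/104 (71.87%, fail) or 85/105 (72.13%, pass).
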